### **6.1.2 Community Health Center Setting**

This intervention is considered modified DOT (mDOT) since between 3-7 weekly doses will be directly observed.

*Method of Observation:* All observed doses will be observed using electronic DOT (eDOT), via the mobile health smartphone app miDOT (developed by emocha Mobile Health, Inc.). Participants will be provided with a smartphone that is pre-loaded with a data/minutes plan and the miDOT app. Research staff will train the participant on how to use the app. Using the app, participants will take a video of themselves taking their HCV medication, then upload the video to the database maintained by emocha. Research staff will review these videos. On the day of medication pick-up, research staff will be available to provide technical assistance with that day's video.

If a participant loses the study-provided phone or is otherwise unable/unwilling to use the miDOT app, participants will receive mDOT three times per week at the CHC by clinic/research staff. The remaining doses will be taken by the participant outside of the clinic.

*Dispensing of Medication:* Participants participating in mDOT will receive their medications in weekly blister packs once a week. Participants will return blister packs (with or without any remaining medication) at their next research visit. If the participant is not using the emocha miDOT app, their medication will be packaged in weekly blister packs and the participant will receive three observed doses at the clinic by clinical or research staff. The blister pack will remain with staff during the week until the participant has received their last observed dose for the week. The participant will then receive the blister pack with remaining doses to take home as unobserved doses. For any unobserved doses during the week prior to their final observed dose of the week, the participant will pop out the pill from the blister pack and take it home in a labeled pill case.

Research or clinic staff will: (i) notify clinicians when doses were declined or not observed and (ii) refer subjects to clinicians as necessary.

**Rescue Doses:** Each participant will receive a container, labeled with the contents, containing up to two doses of HCV treatment medication. In the event the participant misses the opportunity to take an observed dose at the OTP, he/she can take one of the rescue doses instead. This container will be either a pill case or a container specified by the local site. When the participant presents to the program for the next observed dose, the prior missed dose will be given to the participant to replace the rescue dose that was taken for any future events.

**Record keeping:** Research staff will review the miDOT videos, and record the date and time that the dose was taken. For participants not utilizing miDOT, clinic or research staff will observe the participant taking their medication and log the information on a standardized log. Adherence will be measured with standardized forms each week by Study Coordinators and will include pill counts.

Adherence will be measured and logged with standardized forms each week by research staff and will include pill counts of blister packs.

## 6.2 Patient Navigation

The study will follow a PN model developed by New York City Department of Health (DOH) in collaboration with Montefiore Medical Center and the community. HCV PNs have the following functions: 1) coordination of treatment; 2) health education and promotion; 3) assisting patients to overcome barriers; and 4) psychosocial support. Additional support may be offered through optional weekly peer-led support group (see below Section 6.3). Details of the PN protocol and materials are in the Patient Navigator Manual. Implementation of the PN protocol will differ by site based on the structure of the PN groups. Sites will document site-specific procedures in their operating manuals.

### Packing of Pills for Patient Navigation Arm

For the PN arm pills will be packed in two-week blister packs and dispensed every other week. If participant is having difficulty with adherence on the biweekly schedule, the provider will assess changing the dispensing to weekly, and document the reasons for changing. No doses will be observed so even if patient is coming to the clinic weekly and picking up medications, all doses will be self-administered.

## 6.3 Education and Peer Support

### Optional Peer Support - Weekly Support Groups:

Peer support groups may be available at all sites for all participants, depending on local factors. Peer support groups will provide support and education covering the following topics: natural history, goals of treatment, treatment regimen and side effects, adherence (including strategies), drug and alcohol abuse, and transmission / reinfection. Support groups will receive HCV support group materials developed by Project Inform, Montefiore Medical Center, and HCV Mentor and Support Group; each group will be guided by local advisory boards based on local patient preferences and barriers. Availability, structure and frequency of peer support and education will differ by site. Sites will document available peer support and education resources, structure and attendance in a site log.

## 7 Study Procedures/Evaluations

### 7.1 Clinical Evaluations

Individual medical records will be reviewed to evaluate HCV-related labs and dates performed (HCV viral load, genotype and subtype, FIB-4 (AST, ALT, and Platelets), total bilirubin, albumin, prothrombin time, FibroSURE (if available), Fibroscan/liver biopsy (if available), abdominal imaging results (ultrasound/MRI) if available, and other medical history including the most recent HIV test.

To determine presence of cirrhosis, all subjects will have a FIB-4 biomarker test calculated at enrollment (obtained by chart review). If FIB-4>3.25, the patient is considered to have advanced cirrhosis. If available, results of fibroscan, liver biopsy or imaging study (ultrasound/CT/MRI c/w cirrhosis) will be used for stratification instead of FIB-4.

Psychiatric status will be assessed in all participants using structured instruments, including: 1) PHQ-9 to assess for depression and 2) the GAD-7 to assess for anxiety. Suicidal ideation will trigger a psychiatric referral.

### 7.2 Laboratory Evaluations

HCV Viremia: Blood for HCV viral loads will be sent directly to Quest Diagnostics. Twenty mL of blood will be collected at visits 5, 6, 7, 8, 9, 10, 11, 12, 13, 14, 15, 16 and 17 for HCV viremia testing and archiving. Specimens will be identified only by study ID number or bar-code, and will also be labeled with the name of the research study, the date and time of collection, and the specimen number. Each site will send blood samples directly to Quest. Results which will be entered into the study data system.

Resistance testing: For subjects who fail to achieve SVR or show evidence of reinfection, NS5A/NS5B resistance testing will be performed on the baseline, and either treatment failure visit (unscheduled) or Visit 5 specimens. The second time point will be determined by when treatment failure is first identified. The specimen for “treatment failure visit” will be used if the subject fails treatment during the 12 weeks of treatment, and the specimen for “Visit 5” will be used if the subject fails treatment after the treatment period. All specimens for resistance testing will be shipped to Montefiore CRC, and banked. Batched runs for resistance testing will be run at Monogram.

Biorepository specimen: Blood specimens will be collected at research visits 1, 5, 6, 7, 8, 9, 10, 11, 12, 13, 14, 15, 16 and 17. At Visit 1, twenty mL of blood will be drawn and

stored locally until sent to the study biorepository. A biorepository will be established at Prima Health-Upstate for archiving stored blood for future studies. At all other visits, twenty mL of blood will be drawn and sent to Quest for HCV VL testing and temporary archiving before being sent to Prisma Health-Upstate's Biorepository.

Toxicology: Urine toxicology tests (American Bio Medica Corporation RapidTox Point of Care (POC) test) will be performed at research visits 1, 2, 3, 4, 5, 7, 9, 11, 13, 15, and 17. At these research visits, the RA will ask subjects to provide a urine specimen, unobserved, in a private bathroom. Collection containers and biohazard bags will be available to the study staff from the commercial laboratory. Specimens will be labeled with the name of the research study, the date and time of collection, and the specimen number; no names or other identifying information will be used. The specimen number will be generated using the subject's study ID number, the letters UT (to denote urine toxicology test), and the visit number. The RA will perform the point of care test (results back in 5 minutes). Urine will be tested for multiple substances: amphetamines, barbiturate, benzodiazepine, buprenorphine, cocaine, marijuana, methadone, methamphetamine, opiates, and oxycodone. Results will be recorded in REDCap. Urine toxicology results are confidential and will only be used for study purposes, not recorded in the participant's clinical record.

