### **Direct-acting antiviral HCV agents and resistance**

HCV NS5A resistance-associated variants (RAVs) can emerge following unsuccessful treatment with an NS5A-inhibitor containing regimen as they have relatively low barriers to resistance [36]. RAVs with reduced drug susceptibility are also observed in treatment-naïve patients. Patients who did not achieve SVR in Gilead studies evaluating direct-acting antiviral regimens including ledipasvir (but not sofosbuvir) were enrolled in a 3-year registry trial. NS5A RAVs were measured at positions 24, 28, 30, 31, 32, 58, and 93 because they confer >2.5 reduced susceptibility to ledipasvir in-vitro. At baseline, 16% of patients (12/76) of patients treated with ledipasvir had NS5A RAVs. At virologic failure, almost all (99%; 72/73) of patients had NS5A RAVs. Moreover, 86% of these patients still had NS5A RAVs at follow-up week 96 [37]. NS5A mutations seen in monotherapy with velpatasvir include those measured at positions 24, 28, 30, 31, 32, 58, 92, and 93. Cross-resistance is observed to all NS5A inhibitors [38]. NS5A inhibitor-resistant viruses appear to persist for years after treatment failure, and the time needed to clear resistant variants is unknown. Therefore, resistant viruses associated with decreased response to antiviral treatment may be transmitted to other PWID.

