### **HCV reinfection among PWID**

Reinfection is a potential problem and a barrier to treatment among PWID [23]. Data collected to date, principally in PWID who have received interferon-based treatments, show reinfection is low: 5.2/100 person years (py) for those who report injection drug use after treatment, and less (3.2/100 py) for those who do not report ongoing injection drug use [39, 40]. However, recent reports have noted higher rates of reinfection after interferon-based treatments in prisoners (8/100 py), HIV/HCV Men who have Sex with Men (MSM) (24/100 py), and PWID who relapse to drug use with longer follow-up (30/100 py). [41, 42]

Prospective studies assessing HCV reinfection PWID who spontaneously cleared infection [43, 44] show that to accurately capture reinfection events, genotyping and viral sequencing is necessary to distinguish reinfection from intercalation. Without these tests, estimates of reinfection incidence were significantly overestimated. Testing interval also has an impact on detection of reinfection. In PWID who clear infection spontaneously, testing intervals less frequent than every three months resulted in substantial (by up to 66%) underestimation of reinfection rate [45]. A caveat here is that these estimates are from patients who spontaneously clear the virus, and who have

been shown to have a high likelihood of re-clearance of subsequent infections [44, 46, 47], and immunological responses to reinfection may differ in those with treatment induced clearance. Systematic testing (every 3 months after SVR12 in our proposed study) to assess the presence of HCV RNA will be essential to accurately determine reinfection events. There is little to no data on reinfection rates in the era of DAAs.

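### Protocol 7.2 assigns no viremic second specimen to a reinfection first seen after Visit 5, and 11.11 does not specify the by-arm incidence analysis that 3.2 calls for

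*Protocol*

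**What the plan says.** **Specimen rule.** Protocol 7.2 covers participants who do not reach SVR and those who "show evidence of reinfection, NS5A/NS5B resistance testing will be performed on the baseline, and either treatment failure visit (unscheduled) or Visit 5 specimens". It then explains how to choose between the two: "The second time point will be determined by when treatment failure is first identified". The unscheduled specimen serves failure during the 12 weeks of treatment, and Visit 5 serves failure after it. Section 8.7 likewise ties the extra resistance draw to treatment failure. Blood is also drawn at each of Visits 6-17. It is tested for HCV RNA and then stored in a biorepository set up "for archiving stored blood for future studies".

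**Why sequence data are wanted.** Protocol 2.1 warns that "resistant viruses associated with decreased response to antiviral treatment may be transmitted to other PWID". Its reinfection subsection says that "genotyping and viral sequencing is necessary to distinguish reinfection from intercalation". That statement comes from people who cleared the virus spontaneously, and the protocol adds that "immunological responses to reinfection may differ in those with treatment induced clearance".

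**Analysis.** Section 3.2(v) poses two by-arm questions on reinfection, (a) incidence and (b) proportion, and 3.2 promises time-to-event analyses. Section 11.11 provides an exact binomial interval for the proportion and logistic regressions in which arm is an adjustment term. It hypothesises at least 5% reinfection and gives 3.5% to 7.2% as the expected interval at N=540. The SAP analyses SVR, initiation, completion and adherence, and has no reinfection section.

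**Follow-up.** Section 8 plans 144 weeks after SVR12. Section 8.6.9 shows that Visits 14-17 (weeks 132-168) were added later and only for participants who signed a new consent.

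**The concern.** The specimen rule includes reinfections but names only tubes suited to treatment failure. A participant who has SVR at week 24 and becomes viremic later is sent to a tube without detectable virus. The post-reinfection resistance result could then not be obtained, nor could the comparison with baseline that would help to tell late relapse from reinfection. Long-term follow-up exists partly to find these very participants.

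The analysis section answers a different question from the objective. A proportion over mixed follow-up has no time base, so it cannot be set beside the per-person-year rates that the protocol cites. The by-arm incidence question has a named class of analysis but no model, at-risk set, analysis origin or censoring rule. Leaving these open lets them be chosen after the data are seen.

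**Working it through.** **1. Specimen timing.** Visit 5 is week 24 (8.6.1), which is 12 weeks after a 12-week course. For a participant with SVR there:
- Baseline specimen: viremic (an entry criterion in 5.1), so it can be sequenced.
- Treatment-failure specimen: does not exist, as there was no on-treatment failure.
- Visit 5 specimen: no detectable virus.
- Visits 6-17 specimens: drawn and archived, but neither 7.2 nor 8.7 assigns one to the assay. The visit table shows a single mark for the NS5A/NS5B assay, whose column is uncertain after text extraction, so I do not rely on it.

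**2. The plan's own interval.** Input: 5% of 540 = 27. The Wilson interval is [p + z²/2n ± z√(p(1-p)/n + z²/4n²)] / (1 + z²/n), with p = 0.05, n = 540 and z = 1.96:
- centre 0.053557/1.007114 = 0.0532
- half-width 0.018723/1.007114 = 0.0186
- limits 3.46% and 7.18%, which match the stated 3.5% and 7.2%.

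The exact (Clopper-Pearson) method named in 11.11 gives 3.32% to 7.19%. The stated resistance interval (7.7%, 12.8%) shows the same pattern: at 54/540, Wilson gives 7.75% to 12.82% and exact gives 7.60% to 12.85%. The quoted figures are therefore Wilson intervals.

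**3. At-risk set.** Only participants with SVR can be reinfected. With 270 per arm after attrition:
- 80% SVR in both arms: 432
- 80% in PN and 89% in mDOT (the detectable value in 11.10): 216 + 240.3 = 456

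The exact interval for 23/456 is 3.2% to 7.5%, so the change of denominator barely moves the precision.

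**4. Time base of the 5%.** Weeks 24 to 120 are 96 weeks = 1.84 years, and weeks 24 to 168 are 144 weeks = 2.76 years. At a constant rate, r = -ln(0.95)/t:
- 96 weeks: 0.0513/1.84 = 2.8 per 100 person-years
- 144 weeks: 0.0513/2.76 = 1.9 per 100 person-years

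Protocol 2.1 says that earlier data "show reinfection is low: 5.2/100 person years (py) for those who report injection drug use after treatment", and gives 3.2/100 person-years for those who do not report injecting. Both implied rates lie below that range.

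**5. Illustration of the arm comparison.** Assumptions: 456 at risk, constant rate, no loss beyond the planned 10%, 1:1 allocation, two-sided 0.05, 80% power. Cumulative risk = 1 - exp(-rt). Events = 456 × cumulative risk. Detectable ratio = exp[2(1.960 + 0.842)/√events].

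| Rate per 100 py | Weeks | Cumulative | Events | Detectable ratio |
|---|---|---|---|---|
| 3.2 | 96 | 5.7% | 26.1 | 3.00 |
| 5.2 | 96 | 9.1% | 41.6 | 2.38 |
| 3.2 | 144 | 8.5% | 38.5 | 2.47 |
| 5.2 | 144 | 13.4% | 61.0 | 2.05 |

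The 144-week rows assume that everyone re-consented, so they are a best case. The protocol also cites higher rates in some groups, up to 30/100 person-years, at which smaller ratios would be detectable. Section 11.11 states no detectable reinfection difference between arms.

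**The case against.** Several counter-arguments are sound and limit the point.

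- **Blood is not lost.** It is archived at every visit from 6 to 17, and a baseline sequence would exist. A reader might infer that a late reinfection yields no sequence or resistance result at all. The documents do not support that. Only the post-reinfection specimen is unassigned, and it can still be assigned.
- **A starting point is implied.** Protocol 2.1 sets testing every three months after SVR12, and section 8 counts follow-up from SVR12. It would be wrong to say that the plan gives no hint of an origin. It does not define one for analysis.
- **The proportion may be covered.** The logistic model in 11.10 refers to five binary outcomes. It could serve 3.2(v)(b), but not the incidence question in (a).
- **The SAP limits its scope** to SVR and several secondary outcomes, so its silence is not an error in itself. Protocol 11.11 then has to carry the analysis, and it does not.
- **No bias between arms is shown.** Both arms have the same research visits. Mixed follow-up would distort the arm comparison only if loss or re-consent differed by arm, and nothing in the documents says so.
- **Misclassification has no known size.** The sequencing statement rests on spontaneous clearers, as the protocol acknowledges.

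A reader might also infer double counting, since SAP 5.2 lets viral loads 99-365 days after treatment determine SVR, and Visits 6-8 (168, 252 and 336 days after a 12-week course) fall in that window. The algorithm is in SAP Figure 2, which is not shown here, so the inference cannot be made.

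**Conclusion.** Both parts hold in limited form.

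The rule in 7.2, as written, cannot deliver the post-reinfection test it orders for anyone with SVR at Visit 5 who is first viremic later. This is a fault of assignment, not of collection. How many results it would affect, and how much misclassification would follow, cannot be derived from the documents.

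Section 11.11 does not specify the by-arm incidence analysis that 3.2 calls for. Its 5% corresponds to 2.8 or 1.9 per 100 person-years depending on whether follow-up ends at week 120 or 168, assuming a constant rate. The use of 540 rather than those with SVR is a matter of definition with little effect on precision. The detectable ratios of about 2.4-3.0 (96 weeks) and 2.05-2.5 (144 weeks) only illustrate the scale. They rest on 456 at risk, a constant rate and no further loss.

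The point should be corrected, but it concerns a secondary outcome and does not touch the primary SVR comparison.

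**What to change.** **In 7.2 and the visit table:**
- For viremia first seen after SVR, run the same NS5A/NS5B assay on baseline and on the first viremic archived specimen from Visits 6-17.
- Compare the two sequences to help separate late relapse from reinfection.
- Keep Visit 5 for participants viremic at Visit 5.

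**In 11.11:**
- Restrict reinfection to participants with SVR, start time at SVR determination, and censor at the last HCV RNA result.
- Report events per person-year with Poisson intervals by arm.
- Compare arms, with arm as the tested term, in a Poisson model or an interval-censored time-to-event model that reflects 12-weekly testing. Keep the proportion as a supplement.
- Restate the expected rate and precision on that basis, add a detectable rate ratio, and make the quoted interval agree with the named method (3.3% to 7.2% if exact at 27/540).

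**Ask the sponsor to confirm** that the 99-365 day window in SAP 5.2 and the reinfection definition do not overlap.

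**Cost:** wording in two sections and a table; retrieval and shipping of later tubes, with a check that enough stored volume remains; a sequence-comparison step; and modest extra analysis. The later tube replaces the Visit 5 tube, so the number of assays per person ordered by 7.2 does not change.
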